7. RATIONALE AND BACKGROUND

Ulcerative colitis (UC) is a type of inflammatory bowel disease (IBD) characterized by chronic inflammation of the gastrointestinal tract, marked by an abnormal immune response. UC is restricted to the colon and affects the mucosa of the gut¹. As a result of the inflammatory reaction, the intestinal wall is damaged, frequently leading to bloody diarrhea and abdominal pain.

UC presents significant health and socioeconomic burdens for the individual patient and society^{6,7,8}. There is currently no cure for UC¹. Moderate-to-severe UC often requires treatment with systemic agents, such as glucocorticoids and azathioprine⁹, many of which are associated with infectious, cardiovascular, gastrointestinal and malignant adverse events^{10,11}. Tofacitinib, an inhibitor of the Janus kinase (JAK) family of kinases, was approved in the United States (US) in May 2018 at a dose of 5 mg twice daily or 10 mg twice daily for the treatment of adults with moderate-to-severe UC. In July 2019, the US prescribing information (USPI) was updated to note that tofacitinib should be prescribed for adult patients with moderate-to-severe UC who have had an inadequate response or who are intolerant to tumor necrosis factor inhibitors (TNFis). In December 2019, the extended-release formulation was also approved for UC patients at a dose of 11 mg once daily and 22 mg once daily. Use of tofacitinib in combination with biological therapies for UC or with potent immunosuppressants such as azathioprine and cyclosporine is not recommended.

Tofacitinib is also currently approved for three other indications in the US, and these include in adults with moderate-to-severe rheumatoid arthritis (RA) who have had an inadequate response or intolerance to methotrexate (MTX), in adults with active psoriatic arthritis who have had an inadequate response or intolerance to MTX or other disease-modifying antirheumatic drugs (DMARDs), and in patients ≥2 years with active polyarticular course

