9.3.2. Definition of On-Label and Off-Label Use for Assessing Utilization Patterns

The following table summarizes the date tofacitinib was approved in the US and the approved dose for each of the three approved indications.

Table 2. Summary of approved indications and dosages for tofacitinib in the US

Indication	Date approved in the US	Approved dose	Limitations for use	
RA	06 Nov 2012	5 mg immediate-release tablets twice daily	Not recommended for use in combination with biologic	
	24 Feb 2016	11 mg prolonged release tablets once daily	DMARDs or potent immunosuppressants such as azathioprine and cyclosporine	
PsA	14 Dec 2017	5 mg immediate-release tablets twice daily	Not recommended for use in combination with biologic DMARDs or potent immunosuppressants such as azathioprine and cyclosporine	
	14 Dec 2017	11 mg prolonged release tablets once daily		
UC	30 May 2018	5 mg or 10 mg immediate- release tablets twice daily	Not recommended for use in combination with biological	
	12 December 2019	11 mg or 22 mg prolonged release tablets once daily	therapies for UC or potent immunosuppressants such as azathioprine and cyclosporine	
рсЛА	25 September 2020	5 mg immediate-release tablets twice daily or weight-based equivalent twice daily (tablet or oral solution)	Not recommended for use in combination with biologic DMARDs or potent immunosuppressants such as azathioprine and cyclosporine	

pcJIA = polyarticular course juvenile idiopathic arthritis; PsA = psoriatic arthritis; RA = rheumatoid arthritis; UC = ulcerative colitis; US = United States

To evaluate indication for use, all patients' to facitinib use will be classified as onlabel indication, off-label indication or unknown indication associated with the first to facitinib prescription during the observation period. Thus, for the purpose of this analysis, on-label indication for use of tofacitinib will be defined, based on the date of the first prescription, as a prescription of the drug to:

- 1. An adult (patients aged ≥18 years), AND
- 2. After November 2012, a patient whose first tofacitinib prescription occurred after a diagnosis of RA (defined as either as having ≥ 1 inpatient or ≥ 2 outpatient RA diagnosis codes on two unique calendar days, with at least one from a rheumatologist), OR

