- 3. After December 2017, a patient whose first tofacitinib prescription occurred after a diagnosis of PsA (defined as either as having ≥ 1 inpatient or ≥ 2 outpatient PsA diagnosis codes on two unique calendar days, with at least one from a rheumatologist), OR
- 4. Between May 2018 and July 2019, a patient whose first tofacitinib prescription occurred after a diagnosis of UC (defined as the first UC diagnosis code from an inpatient visit or after the second UC diagnosis code from an outpatient visit), OR
- 5. After July 2019, a patient whose first tofacitinib prescription occurred after a diagnosis of UC (as defined above) AND after evidence of prior TNFi use (i.e. using all available data, a prescription for ≥1 TNFi agent prior to first tofacitinib prescription), OR
- 6. After September 2020, a patient aged ≥2 years whose first tofacitinib prescription occurred after a diagnosis of pcJIA (defined as either as having ≥ 1 inpatient or ≥ 2 outpatient pcJIA diagnosis codes on two unique calendar days, with at least one from a rheumatologist)

In contrast, off-label indications will be defined as use of tofacitinib among patients with other diagnoses (i.e. lack of diagnosis codes for RA, PsA, UC or JIA) not fulfilling any of the conditions outlined above. If off-label use among non-approved indications occurs, it is expected that tofacitinib will be more likely used among patients with other non-approved rheumatic conditions (e.g. psoriasis, ankylosing spondylitis) or other non-approved IBD conditions (e.g. Crohn's disease). Thus off-label indications will be identified by broadly targeting diagnosis codes for other non-approved rheumatic and IBD conditions. Additionally, if the indications for which tofacitinib is prescribed cannot be determined from the available data, these will be classified as unknown indications and will evaluated separately as described in Section 9.7.1.

Among patients with on-label indications, to facitinib dose will be assessed. For each of these patients, every to facitinib prescription will be classified as on-label or off-label based on the labeled dose for the patient's indication at the time of prescription. Thus, for the

purposes of this analysis, on-label dose of tofacitinib will be defined, based on each tofacitinib prescription, using the following criteria:

- 1. Between November 2012 and November 2017, a prescription of tofacitinib 5 mg twice daily occurring only after a diagnosis of RA (as defined above)

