9.3.6. Endpoints of Interest

To assess tofacitinib utilization patterns, the main endpoint of interest to be captured in the interim and final study reports will be the indication for tofacitinib use, classified as on-label, off-label, or unknown, based on medical events (diagnoses and/or medication use) identifiable around the time of the first ever tofacitinib prescription. The date of first prescription of tofacitinib during the study period is the index date as described in Section 9.3.4.1. All patients' tofacitinib use will be classified as on-label indication, off-label indication or unknown indication according to the first prescription of tofacitinib received, regardless of later prescriptions. The on-label, off-label and unknown indication classifications will be made based on the authorized indication(s) as of the index date.

For the active surveillance portion of the study, the safety events of interest (to be defined via ICD-code based algorithms in the SAP) which will also be captured in the interim and final study reports include the following:

- Malignancy, excluding NMSC
- Lung cancer
- Lymphoma
- NMSC
 - Serious infections
 - Opportunistic infections (e.g. tuberculosis)
 - HZ reactivation

- MACE
- VTE (DVT and PE)
- Myocardial Infarction (MI)
- Hepatic events
- PML (PML)
- GI perforations
- ILD
- Fractures
- Surgery for UC (e.g. colectomies, partial colectomies, and proctocolectomies; full list of procedures to be detailed in SAP)
- Death

Of note, due to limitations related to the Marketscan database, only in-hospital deaths can be captured (outcome will be defined via an algorithm currently under development, details of which will be outlined in the SAP). Deaths occurring in other environments such as home, non-hospital institutions, etc., cannot be captured.

The above list of safety endpoints may be extended with additional sub-diagnoses or new health-related outcomes as agreed to by study researchers and Sponsor before the interim reports and final study report. These decisions will be made prior to initiation of analyses and documented in the SAP kept on file by the Sponsor.

In addition, the final study report will include the number of tofacitinib-exposed pregnancies.

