9.7.1. Assessment of tofacitinib utilization patterns

Categorical variables will be summarized using frequencies and proportions; continuous variables will summarized using means with standard deviations and/or medians with interquartile ranges, as appropriate. Age will be reported as a continuous variable and in clinically relevant categories, to identify off-label pediatric use (e.g. use in patients younger than 18 years prior to September 2020 and who do not have a pcJIA diagnosis) and use among elderly patients (i.e. 65 years or older).

The proportions of patients with an on-label, off-label, or unknown tofacitinib indication will be estimated with corresponding 95% confidence intervals (CIs). Patients who are prescribed tofacitinib for on-label, off-label and unknown indications will be described in terms of demographics (age, sex), comorbidities, prior and current medications (in terms of comedications not recommended for use while on tofacitinib i.e. biologic DMARDs, biologic therapies for UC or potent immunosuppressants such as azathioprine and cyclosporine as described in Table 2), as well as prescribed DD and duration of tofacitinib therapy. As it is expected that tofacitinib is more likely to be used off-label in non-approved rheumatic (e.g. psoriasis, ankylosing spondylitis) and IBD conditions (e.g. Crohn's disease), to identify off-label indications, diagnosis codes for other non-approved rheumatic and IBD conditions will be targeted. Among patients with on-label (approved) indications (i.e. RA, PsA, UC, pcJIA), tofacitinib dose will be assessed (as described in Section 9.3.2) and classified as on-label dose or off-label dose according to each prescription of tofacitinib. The proportion of tofacitinib prescriptions with off-label dosing, stratified by approved indication, will be estimated.

To further assess on-label/off-label use of tofacitinib, the proportion of TNFi-naïve UC patients prescribed tofacitinib prior to 01 July 2019 (on-label) and post 01 July 2019 (off-label) will also be estimated and described. Additionally, to further understand off-label dosing among patients with non-UC approved indications such as RA, PsA and pcJIA, the proportions of non-UC patients on 10 mg twice daily/22 mg once daily therapy will also be estimated and reported.

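### The on-label / off-label / unknown endpoint leaves some users in no class, including TNFi-naive UC starters after July 2019, whom Section 9.7.1 itself calls off-label

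*Protocol*

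**What the plan says.** Section 9.3.6 states that "the main endpoint of interest to be captured in the interim and final study reports will be the indication for tofacitinib use", in three classes, and that the "classifications will be made based on the authorized indication(s) as of the index date". Section 9.3.2 says every user is to be placed in one of the classes, according to the first prescription.

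The classes are defined in Section 9.3.2:

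- **On-label.** Adult age plus one of five dated rules. RA counts from November 2012 (rule 2) and PsA from December 2017 (rule 3). UC counts on diagnosis alone between May 2018 and July 2019 (rule 4), and after July 2019 only with a prior TNFi prescription (rule 5). pcJIA counts from September 2020 (rule 6).
- **Off-label.** "use of tofacitinib among patients with other diagnoses (i.e. lack of diagnosis codes for RA, PsA, UC or JIA", with a closing clause that such patients satisfy none of the listed conditions. The next step is: "Thus off-label indications will be identified by broadly targeting diagnosis codes for other non-approved rheumatic and IBD conditions".
- **Unknown.** "if the indications for which tofacitinib is prescribed cannot be determined from the available data, these will be classified as unknown indications".

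Section 9.7.1 separately reports TNFi-naive UC users "prior to 01 July 2019 (on-label) and post 01 July 2019 (off-label) will also be estimated and described".

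On prior treatment, Section 7 describes the RA indication as covering adults "who have had an inadequate response or intolerance to methotrexate (MTX", and the PsA indication as following MTX or other DMARDs. The RA rule reads "After November 2012, a patient whose first tofacitinib prescription occurred after a diagnosis of RA" and the PsA rule has the same form. Neither asks for earlier treatment.

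**The concern.** A classification that is to cover all users needs classes that are exhaustive. Here, failing the on-label rules is not enough to be off-label: the patient must also have no code for any approved disease. Anyone with an approved disease who was treated outside its approval date or its TNFi condition therefore has no class.

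The proportions in the three classes answer Research Question 1. Patient characteristics, daily dose and duration of therapy are reported by the same classes (Sections 9.3.3 and 9.7.1), so unclassed users drop out of those tables too, or are placed by a decision that the protocol does not record. The group most clearly affected, TNFi-naive UC users after the 2019 label change, is one that the study names as an objective.

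**Working it through.** The protocol states no figure for this endpoint, so there is nothing to reproduce. The check is to run cases through the Section 9.3.2 rules.

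| First tofacitinib user | On-label? | Off-label? | Unknown? | Result |
|---|---|---|---|---|
| UC adult, 2021, prior TNFi | yes (rule 5) | no | no | on-label |
| UC adult, December 2018, TNFi-naive | yes (rule 4) | no | no | on-label |
| UC adult, 2021, TNFi-naive | no (fails rule 5) | no (UC code) | no | **no class** |
| UC adult, 2016 | no (before approval) | no (UC code) | no | **no class** |
| PsA adult, 2016 | no (before approval) | no (PsA code) | no | **no class** |
| Crohn's disease adult, 2021 | no | yes | no | off-label |
| No relevant code | no | no | yes | unknown |

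Section 9.7.1 calls the third case off-label. Section 9.3.6, which looks to authorization at the index date, implies the same for the fourth and fifth.

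**Direction of the error.** Let N be all users, O those captured as off-label and M those with no class who should be off-label. The intended proportion is (O + M)/N.

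- If unclassed users stay in the denominator, or are put in another class, the report shows O/N, which is lower by M/N.
- If they are dropped, it shows O/(N − M). Cross-multiplying, (O + M)(N − M) − O·N = M(N − O − M). This is positive whenever M > 0 and anyone is on-label or unknown, so the result is again too low.

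Illustration with assumed shares O = 5% and M = 3% of N: intended 8%; reported 5% if kept, or 5/97 = 5.15% if dropped.

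**Scale.** The protocol gives no split by indication or prior therapy, so M cannot be computed. Section 9.5 gives 11,857 users in 2016–2018. The 95% half-width of a proportion is 1.96 × √(p(1 − p)/11,857):

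- p = 50%: 0.90 points
- p = 5%: 0.39 points

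For assumed M of 1%, 3%, 5% or 10%, the number affected would be 119, 356, 593 or 1,186. Above about 1%, the misclassification exceeds the sampling error. These data predate July 2019, so they serve for scale only.

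**The July 2019 boundary.** Rules 4 and 5 meet at July 2019 without a day. A TNFi-naive UC patient first dispensed in mid-July 2019 is on-label if rule 4 is read to include July, and off-label under Section 9.7.1.

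**The case against.** The strongest defence is that the off-label sentence ends with a clause about meeting none of the listed conditions, which could be meant as a catch-all, and that Sections 9.3.6 and 9.7.1 show the intended result. The intention is indeed clear. But the clause qualifies patients already restricted to having no RA, PsA, UC or JIA code, and the sentences after it look for off-label use only through codes of other conditions. A programmer following the text would not recover these patients.

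It is also fair that TNFi-naive UC users have their own objective and are reported separately in Section 9.7.1, so that group stays visible in the report. This limits the harm but does not repair the three-way endpoint, and it does nothing for use before approval.

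Three stronger readings are tempting, and the documents do not support them.

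- **That unknown is inflated.** Unknown is limited to indications that cannot be determined, and a UC-coded patient's indication can be.
- **That RA and PsA on-label use is overstated by a stated amount.** Rules 2 and 3 do omit the MTX and DMARD conditions of Section 7. However, they are openly operational definitions, inadequate response is not visible in claims, and the utilization study sets no minimum enrollment (Section 9.2.1.1) and no exclusions (Section 9.2.2). Absence of a prior claim may simply reflect short look-back. Any figure in points would need the RA/PsA share and the share without prior treatment, and the protocol gives neither.
- **That most UC users are affected because most of the period lies after the label change.** July 2019 to June 2025 is 72 of about 85 months since UC approval, but that is calendar time, not a share of patients.

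**Conclusion.** The definition is wrong as written. Its classes do not cover all users, and it contradicts Section 9.7.1 for TNFi-naive UC starters after July 2019 and Section 9.3.6 for UC and PsA use before approval. The off-label proportion is understated; the amount cannot be derived from the protocol. The date mismatch in rules 4 and 5 is a smaller fault confined to about one month of first fills.

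The conclusion rests on reading the off-label sentence as it stands and on treating a UC or PsA diagnosis that meets the protocol's own coding rule as a determinable indication. It is not a matter left to the SAP: the rules are fixed in the protocol, and Section 9.7 requires an amendment for major changes to endpoint definitions. The RA/PsA prior-treatment question supports a supplementary analysis and no more.

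**What to change.** In Section 9.3.2:

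1. Define off-label indication as any determinable indication, including RA, PsA, UC or pcJIA, that meets none of the on-label rules on the index date. The search for codes of other conditions stays as one route into this class, not the only one.
2. Keep unknown for indications that cannot be determined.
3. Use the 01 July 2019 cut of Section 9.7.1 in rules 4 and 5, and state on which side the day itself falls.

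As a supplementary analysis, report the RA and PsA on-label proportion when a prior MTX claim (RA) or a prior MTX or other DMARD claim (PsA) is also required, using all available data as rule 5 does for TNFi. Keep the diagnosis-only proportion primary, because short look-back hides some earlier use.

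The cost is a text amendment, a change to the classification code and one further claims look-up. No new data are needed, and the final report is due on 30 June 2026. Both interim reports were scheduled before this protocol version, so the final report should say whether their proportions used a different rule.

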- 2. Between February 2016 and November 2017, a prescription of tofacitinib 11 mg once daily occurring only after a diagnosis of RA (as defined above)
- 3. After December 2017, a prescription of tofacitinib 5 mg twice daily or 11 mg once daily occurring only after a diagnosis of either RA or PsA (as defined above)
- 4. After May 2018, a prescription of tofacitinib 5 mg twice daily occurring only after a diagnosis of either RA, PsA or UC (as defined above)
- 5. After May 2018, a prescription of tofacitinib 10 mg twice daily occurring only after a diagnosis of UC (as defined above)
- 6. After December 2019, a prescription of tofacitinib 11 mg once daily or 22 mg once daily occurring only after a diagnosis of UC (as defined above)
- 7. After September 2020, a prescription of tofacitinib 5 mg twice daily occurring only after a diagnosis of RA, PsA, UC or pcJIA.

For each approved indication of tofacitinib (i.e. RA, PsA, UC, pcJIA), the proportion of tofacitinib prescriptions with off-label dosing will be estimated as described in Section 9.7.1.

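### Section 9.3.2 lists a weight-based pcJIA dose as approved in Table 2, but its on-label dose rule accepts only 5 mg twice daily

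*Protocol*

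**What the plan says.** Three parts of Protocol Section 9.3.2 bear on the pcJIA dose.

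- Table 2, the section's summary of approved indications and doses, gives for pcJIA, from 25 September 2020: "5 mg immediate-release tablets twice daily or weight-based equivalent twice daily (tablet or oral solution").
- The text before the dose criteria says that, for patients with an on-label indication, every prescription "will be classified as on-label or off-label based on the labeled dose" for that indication at that time. The lead-in to the list then makes the list the definition: "purposes of this analysis, on-label dose of tofacitinib will be defined, based on each tofacitinib prescription, using the following criteria".
- Of the seven items that follow, only item 7 names pcJIA: "After September 2020, a prescription of tofacitinib 5 mg twice daily occurring only after a diagnosis of RA, PsA, UC or pcJIA".

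Section 7 (Rationale and Background) states that 5 mg twice daily is the only approved pcJIA regimen. The abstract likewise gives 5 mg twice daily and no alternative.

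The proportion of prescriptions with off-label dosing, by approved indication, is a planned output in Sections 9.1, 9.3.2 and 9.7.1, and Section 9.3.2 names pcJIA as one of the indications.

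**The concern.** The dose rule is narrower than the approved dose it is meant to represent. A prescription that follows Table 2 at a weight-based dose other than 5 mg twice daily would be counted as off-label dosing.

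The pcJIA stratum would then mix real departures from the label with doses that the protocol itself lists as approved. The error runs one way: it can raise apparent off-label dosing but cannot lower it. The weight-based alternative matters most for children, so a report to regulators could show off-label dosing in a pediatric indication that comes only from how the rule is worded.

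**Working it through.** No figure in the protocol needs reproducing; the check is a comparison of texts followed by simple arithmetic.

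**Which doses the seven items accept (Section 9.3.2)**

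| Item | Doses accepted | Diagnoses named |
|---|---|---|
| 1 | 5 mg twice daily | RA |
| 2 | 11 mg once daily | RA |
| 3 | 5 mg twice daily, 11 mg once daily | RA, PsA |
| 4 | 5 mg twice daily | RA, PsA, UC |
| 5 | 10 mg twice daily | UC |
| 6 | 11 mg or 22 mg once daily | UC |
| 7 | 5 mg twice daily | RA, PsA, UC, pcJIA |

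One item of seven names pcJIA, and none accepts a weight-based dose. A patient with pcJIA and no RA, PsA or UC can be on-label by dose only through item 7. Item 7 names no formulation, so oral solution at 5 mg twice daily passes. The doses affected are those that are weight-based and differ from 5 mg twice daily.

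**Whether children reach the rule.** Dose is assessed only in patients with an on-label indication. Indication item 1 reads "An adult (patients aged ≥18 years), AND", but item 6 sets its own age limit: "After September 2020, a patient aged ≥2 years whose first tofacitinib prescription occurred after a diagnosis of pcJIA". Section 9.7.1 gives as its example of off-label pediatric use "use in patients younger than 18 years prior to September 2020 and who do not have a pcJIA diagnosis", which leaves out children with pcJIA after that date. Read together, children with pcJIA are meant to count as on-label by indication, so their doses are classified.

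**How long it applies.** From 25 September 2020 (Table 2) to 30 June 2025 (end of data collection) is 1,739 days, and 1,739 / 365.25 = 4.76 years. Item 7 is the only pcJIA dose item throughout.

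**Size.** Let d be the share of pcJIA prescriptions that truly depart from Table 2, and w the share at an approved weight-based dose other than 5 mg twice daily.

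- Proportion off-label under Table 2: d
- Proportion off-label under item 7: d + w
- Part of the reported proportion that is artefact: w / (d + w)

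The protocol gives neither d nor w, so all values below are assumptions.

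| d | w | Reported, d + w | Artefact, w / (d + w) |
|---|---|---|---|
| 5% | 0% | 5% | 0% |
| 5% | 5% | 10% | 50% |
| 5% | 20% | 25% | 80% |
| 5% | 40% | 45% | 89% |
| 10% | 0% | 10% | 0% |
| 10% | 5% | 15% | 33% |
| 10% | 20% | 30% | 67% |
| 10% | 40% | 50% | 80% |

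The only tofacitinib patient count in the protocol (11,857, from 2016–2018 data) predates the pcJIA approval and covers all users, so it cannot size this stratum.

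**The case against.** **The SAP may settle it.** Section 9.3 calls itself a summary, Section 9.3.3 and the dosing comment in the Annex 2 checklist defer detail to the SAP, and Section 9.7 allows the SAP to modify the plan. The SAP is not at hand, so misclassification in the actual analysis cannot be shown. That limits what can be said about the consequence. It does not remove the conflict: item 7 is a written-out rule and not a gap left for later detail.

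**The labeled-dose principle could reconcile the texts.** An analyst guided by the sentence before the list might take 5 mg twice daily to include its weight-based equivalent. But the list is stated to be the definition, and Section 7 says that only 5 mg twice daily is approved for pcJIA, which tells against reading item 7 as shorthand.

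**A strict reading of indication item 1 keeps children out.** If the adult condition governs the whole list, children never reach the dose rule. That reading empties item 6 of its age limit of 2 years and does not fit the pediatric example in Section 9.7.1.

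**Table 2 may be the text in error.** It stands alone against Section 7, the abstract and item 7, and the protocol by itself cannot show which matches the label. This stands as a caution. Table 2 is nevertheless the more detailed statement and the section's declared summary of approved doses, and one of the two texts must change in either case.

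**The size is assumed and the reach is small.** Both are true. The range includes no effect at all, and only one stratum of one descriptive proportion is touched.

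**Conclusion.** The concern holds: the dose rule and the approved-dose table in Section 9.3.2 cannot both be applied to pcJIA. Taking Table 2 as the reference, item 7 overstates off-label dosing in the pcJIA stratum by exactly w. The direction is certain; the amount is unknown and is zero if no such doses appear in the data.

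The scope is narrow. The affected proportion is not itself a Section 8 objective, although it bears on Research Question 1. The Section 8 objective on non-UC dosing concerns 10 mg twice daily and 22 mg once daily and does not change. The RA, PsA and UC strata, the indication endpoint and all safety incidence rates also stay as they are. This should be corrected before the final report, but it does not threaten the study's main results.

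**What to change.** - **Make item 7 a pcJIA-only criterion that mirrors Table 2:** after September 2020 and following a pcJIA diagnosis, accept 5 mg twice daily or the weight-adjusted twice-daily dose, in either tablet or solution form. Nothing is lost for the other indications, because item 4 already covers them: "After May 2018, a prescription of tofacitinib 5 mg twice daily occurring only after a diagnosis of either RA, PsA or UC".
- **Bring Section 7 and the abstract into line with Table 2,** after confirming Table 2 against the label.
- **Add one row to the pcJIA dosing table.** Section 9.3.1 does not list body weight, so weight equivalence cannot be verified. Prescriptions at doses other than 5 mg twice daily that could be weight-based should be shown separately, with a note saying so. Treating these as doses below 5 mg is an assumption to check against the label, because the protocol does not give the weight-based doses.

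The cost is one reworded criterion, two matching text edits and one table row, with no new data. The drawback is that some true under-dosing cannot be told apart from weight-based dosing, which the separate row makes visible.
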